8.3.3 Follow-up of AEs and SAEs

After the initial AE/SAE report, the investigator is required to proactively follow each participant at subsequent visits/contacts, unless a participant or parents / legally acceptable representatives refuses further contact. All AEs that are considered by the investigator as serious, or related to the study intervention administered, or that led to study or vaccination discontinuation, or AEs of special interest (as defined in Section 8.3.6), will be followed during the conduct of the study until resolution, stabilization, or the participant is lost to follow-up (as defined in Section 7.3). For related SAEs ongoing at last study visit, such follow-up may need to continue after the end of the study.

Further information on follow-up procedures is provided in Appendix 10.2.

8.3.4 Regulatory Reporting Requirements for SAEs

- Prompt notification by the investigator to the Sponsor of an SAE is essential so that legal obligations and ethical responsibilities towards the safety of participants and the safety of a study intervention under clinical investigation are met.
- The Sponsor has a legal responsibility to notify both the local regulatory authority and other regulatory agencies about the safety of a study intervention under clinical investigation. The Sponsor will comply with country-specific regulatory requirements relating to safety reporting to the regulatory authority, Institutional Review Boards (IRB)/Independent Ethics Committees (IEC), and investigators.
- An investigator who receives an investigator safety report describing a SAE or other specific safety information (eg, summary or listing of SAEs) from the Sponsor will review and then file it and will notify the IRB/IEC, if appropriate according to local requirements.
- Investigator safety reports must be prepared for suspected unexpected serious adverse reactions (SUSAR) according to local regulatory requirements and Sponsor policy and forwarded to investigators as necessary.

8.3.5 Pregnancy

Not applicable as the study does not include women of childbearing potential.

8.3.6 Adverse Events of Special Interest

AESIs will be captured as SAEs. These include new onset of GBS, encephalitis/myelitis, including transverse myelitis, Bell's palsy, optic neuritis, brachial neuritis, thrombocytopenia, vasculitis, and anaphylaxis.

8.3.7 Medically Attended Adverse Events

MAAEs will be collected using the same process as other AEs. See Appendix 10.2.1 for definition of MAAEs.

8.3.8 Early Safety Data Review

- An ESDR conducted by the SMT will be performed, the goal of which is to allow for a cautious, stepwise approach to vaccine administration. An initial safety review for this study is planned when approximately 10% of participants aged 3 to 8 years are vaccinated and have provided safety data for 7 days after administration of the first dose.
- The safety data collected will be entered into the CRB and will be summarized and reviewed by the Sponsor. It is understood that this review will be based on preliminary data that would not have been subject to validation and database lock.

- The following safety parameters collected from D01 to D08 will be assessed as part of the ESDR review in a blinded manner by the Sponsor:
 - Immediate reactions
 - Solicited injection site and systemic reactions
 - Unsolicited AEs reported as related by the investigator
 - SAEs (including AESIs)
- Enrollment will not be paused during the Sponsor review. Case unblinding may occur if necessary.
- If any of the following criteria are met, a decision will be made by the Sponsor as to whether enrollment in the study will be paused and will be allowed to resume later:
 - An SAE (including AESI) considered as related to the vaccination by the investigator and Sponsor
 - > 10% of participants experiencing any Grade 3 AEs within 7 days after vaccination
- After the ESDR will be conducted, the team will continue to monitor the safety of all participants via SMTs and/or data review meetings during the conduct of the study. SMT periodicity will be detailed in the SMT charter.

8.4 Pharmacokinetics

Pharmacokinetics parameters are not evaluated in this study.

8.5 Genetics

Genetics are not evaluated in this study.

8.6 Biomarkers

No other biomarkers than those described in the immunogenicity assessments section (Section 8.1.2) are evaluated in this study.

8.7 Immunogenicity Assessments

See Section 8.1.2.

8.8 Medical Resource Utilization and Health Economics

Medical Resource Utilization and Health Economics parameters are not evaluated in this study.

8.9 Leftover Biological Samples and Use of Data

Any unused part of the biological samples collected for this study (blood samples) are being retained in long-term storage to support answers to regulatory questions related to the product's licensure and the potential revalidation of the study results.

In addition, parents / legally acceptable representatives will be asked to indicate in the ICF whether they will permit the future use of any unused stored biological samples for other tests and the corresponding data, unless prohibited by local laws or IRBs/IECs (in such case, consent for future use of any unused biological samples will not be included in the site-specific ICF). If they refuse permission, the biological samples will not be used for any testing other than that directly related to this study. If they agree to this future use, they will not be paid for giving permission. Data and samples will be used in compliance with the information provided to participants in the ICF Part 2 (future research). The aim of any possible future research is unknown today, and may not be related to this particular study. It may be to improve the knowledge of vaccines and their mechanism of action, the knowledge of infectious diseases, or to improve existing tests or develop new tests to assess vaccines, or to help identify new vaccine targets or biomarkers that predict participant response to the vaccine. Such research may also include, but is not limited to, performing assessments on DNA, RNA, proteins or metabolites. If future research on genetic material is performed, a specific individual consent will be obtained.

All study participant data and biological samples will be coded such that no direct identifiers will be linked to participants. Coded data and biological samples may be transferred to a Sponsor site (or a subcontractor site), which may be located outside of the country where the study is conducted. The Sponsor adopts safeguards for protecting participant confidentiality and personal data (see Section 10.1.4).

The biological samples will be securely stored at the Sanofi Pasteur laboratory up to 25 years after the end of the study. Any samples remaining at the end of retention period will be destroyed. If a participant requests destruction of his/her samples before the end of the retention period, the investigator must notify the Sponsor (or its contract organization) in writing. In such case, samples will be destroyed and sample related coded data will be anonymized unless otherwise required by applicable laws.

Study participant coded data will be stored for future research for up to 25 years after the end of the study. If data are still considered of important scientific value after this period, coded data already available will be anonymized unless otherwise required by applicable laws (the same will apply to the data of a study participant who has requested the destruction of his/her samples).

Participant's coded data sets provided to researchers for a specific research project will be available to the researchers for a maximum of 2 years after the end of their specific project (end of project is defined by publication of the results or finalization of the future research project report).

Note: The other biological samples collected to qualify the participant for inclusion in the study or to monitor his/her health during the study are dedicated for immediate use. If any of these biological samples are not completely used up, they will be destroyed at the latest at the end of the study or after the time requested by local law.

9 Statistical Considerations

All statistical analyses will be performed under the responsibility of the Sponsor's Biostatistics Platform using the SAS® software, Version 9.4 or above.

The core SAP will be written, and peer reviewed before the initiation of the study. In accordance with the protocol, the SAP will describe all analyses to be performed by the Sponsor and all the conventions to be taken.

It was decided to add to the statistical analysis initially planned, an interim analysis at the end of 2022-2023 season, to evaluate safety and calculate separate PPoS for each of the 8 NI statistical tests included in the primary objective. Creating consequently the possibility of stopping this study if warranted.

More details are given in the interim analysis section below, and complete details will be included in the SAP of this study.

For descriptive purposes, the following statistics will be presented:

Baseline characteristics and follow-up description	Categorical data	Number and percentage of participants		
	Continuous data	Mean, standard deviation, quartiles, minimum, and maximum		
Safety results	Categorical data	Solicited and biological safety: Number and percentage (95% CIs) of participants		
		Unsolicited: Number and percentage (95% CIs) of participants, and number of events		
	Continuous data	At least mean, standard deviation, minimum, and maximum		
Immunogenicity results Categorical data (seroprotection, seroconversion, cutoff)		Number and percentage (95% CIs) of participants		
	Continuous data	Log10: Mean and standard deviation		
	(titer / data)	Anti-Log ₁₀ (work on Log ₁₀ distribution, and anti-Log ₁₀ applied): Geometric mean, 95% CI of the geometric mean, quartiles, minimum, and maximum		
		Graphical representation by reverse cumulative distribution curve (RCDC)		

Table 9.1: Descriptive statistics produced

9.1 Statistical Hypotheses

Primary Objective:

Statistical Methodology for analyzing the primary 8 endpoints of GMTs and SC rates.

Non-inferiority of RIV4 as compared to IIV4 in participants 3 to 8 years of age will be conducted for GMTs and SC rates.

Since all 8 hypotheses have to be rejected at 0.025 significance level, no formal adjustment for multiplicity is necessary.

For each strain, the non-inferiority methodology will be applied to compare the post-vaccination GMTs and the SC rates between the groups using a 1-sided Type I error rate of 0.025 with the given individual hypothesis.

The primary analysis will be conducted into 2 steps starting with testing for NI of GMTs between RIV4 and IIV4. If NI of GMTs based on the 4 strains is demonstrated, then NI for SC will be also tested.

Step1: Geometric Mean Titers

For each of the 4 strains, the hypotheses are as follows. Each of the 4 individual H0 need to be rejected to demonstrate NI in GMTs.

H₀: GMT _{RIV4} /GMT _{IIV4} \leq 0.667 H_A: GMT _{RIV4} /GMT _{IIV4} > 0.667

or equivalently,

H₀: $\log_{10} (GMT_{RIV4}) - \log_{10} (GMT_{IIV4}) \le \log_{10} (0.667)$ H_A: $\log_{10} (GMT_{RIV4}) - \log_{10} (GMT_{IIV4}) \ge \log_{10} (0.667)$

Step 2: Seroconversion

For each of the 4 strains, the hypotheses are as follows. Each of the 4 individual H0 need to be rejected to demonstrate NI in SCs.

H₀: P _{RIV4} - P _{IIV4} \leq -10% H_A: P _{RIV4} - P _{IIV4} > -10%

Secondary Objectives:

There are no statistical hypotheses to be tested in the secondary objectives.

9.2 Sample Size Determination

A total of approximately 1200 evaluable participants 3 to 8 years of age will be assessed (approximately 50% participants enrolled in the age group 3-5 years and 50% participants enrolled in the age group 6-8 years) in this study. Approximately 50% of participants enrolled within age group will be primed, and the other 50% will be unprimed.

Assuming similar GMTs in both groups, a one-sided alpha of 0.025 and a standard deviation of log_{10} titers of 0.6 with a NI margin of 1.5 (or 1/1.5 = 0.667); NI for GMTs would be demonstrated with a study power of approximately 99.6%.

Assuming in each vaccine group the same expected SC rates (0.5, 0.5, 0.7, 0.7) for each of the 4 strains (A/H1N1, A/H3N2, B/Yamagata and B/Victoria), based on conservative estimates from historical data, and a NI margin of 10%, the NI for SC can be demonstrated with a study power of approximately 82.0% (93.7%, 93.7%, 96.7% and 96.7% for each strain, respectively).

Hence, the overall study power is estimated to be approximately 82.0% (82.0% = 99.6%[GMTs] x 82.0%[SC]).

As shown above, to keep the study power above 80%, the sample size was increased accordingly, to have an overall Type II error < 20% for the 8 NI tests.

Assuming 15% attrition rate in this age group; a total of approximately 1412 participants 3 to 8 years of age will be enrolled in this study.

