4.1 Overall Design

The design of the study is summarized in Table 4.1.

Table 4.1: Overall design

Type of design	Parallel, multi-center
Phase	Phase III
Control method	Active-controlled Control Product = Fluarix [®] Quadrivalent (or other commercial names), Egg-based Influenza vaccine (split virion, inactivated) (IIV4) (GlaxoSmithKline Biologicals)
Study population	Healthy children aged 3 to 8 years
Level and method of blinding	Modified double-blind (participant, Sponsor, and Investigator blinded)
Study intervention assignment method	Randomization and stratification by site, age, group and previous vaccinal status for influenza
Number of participants	Approximately 1412 participants 3 to 8 years of age (approximately 50% participants in the age group 3-5 years and 50% participants in the age group 6-8 years, and approximately 50% participants previously vaccinated and 50% participants previously unvaccinated in each age group)
Intervention groups	Randomization in a 1:1 ratio to receive either RIV4 or IIV4. Participants will receive either 1 or 2 doses 28 days apart of either RIV4 or IIV4 depending on whether they were previously vaccinated against influenza or previously unvaccinated against influenza, respectively

Total duration of study participation	Approximately 6 months for participants previously vaccinated against influenza and approximately 7 months for participants previously unvaccinated against influenza
Countries/Region	USA and Europe
Use of an Independent Data Monitoring Committee, Dose Escalation Committee, or similar review group	Safety Management Team (SMT)

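### The overall-power equation in Protocol 9.2 and SAP 3.2 does not hold as printed: 99.6% x 82.0% is 81.7%, not 82.0%; the design is unaffected.

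*Protocol*

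**What the plan says.** Protocol 9.2 sets the basis: "A total of approximately 1200 evaluable participants 3 to 8 years of age will be assessed". Section 4.1 gives the allocation: "Randomization in a 1:1 ratio to receive either RIV4 or IIV4". Together these mean 600 evaluable participants per arm.

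The power statement in 9.2 then has three parts.

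- **GMT step.** "Assuming similar GMTs in both groups, a one-sided alpha of 0.025", with an SD of log10 "titers of 0.6 with a NI margin of 1.5 (or 1/1.5 = 0.667"), leads to "NI for GMTs would be demonstrated with a study power of approximately 99.6"%.
- **SC step.** "Assuming in each vaccine group the same expected SC rates (0.5, 0.5, 0.7, 0.7) for each of the 4 strains" "and a NI margin of 10%, the NI for SC can be demonstrated with a study power of approximately 82.0"%. The per-strain powers are given as 93.7%, 93.7%, 96.7% and 96.7%.
- **Overall.** Power is put at approximately 82.0%, and the parenthesis shows the derivation: "82.0% = 99.6%[GMTs] x 82.0%[SC"].

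The next sentence of 9.2 relies on this result to say that power stays above 80%, that is, that the overall Type II error for the eight tests is below 20%. SAP 3.2 carries the same figures and the same equation.

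**The concern.** The equation has the form x = 0.996x, which cannot hold for a positive x. The overall figure is numerically the same as the SC-only figure, although the plan also requires all four GMT tests to succeed. This is the one line that supports the statement that power exceeds 80%, and it appears in both documents. If the error were large, or if a component power were also wrong, the basis for 1412 participants would be in doubt. The components therefore need checking as well as the final product.

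**Working it through.** **Inputs** (Protocol 9.2 unless noted): 600 evaluable per arm; one-sided alpha 0.025 per test; SD of log10 titer 0.6; GMT margin 1/1.5; SC rates 0.5, 0.5, 0.7, 0.7 in both arms; SC margin 10 percentage points; Wilson score interval for the rate difference without continuity correction (Protocol 9.4.2); 15% attrition.

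**1. GMT power.**
- Standard error = 0.6 x sqrt(2/600) = 0.03464. The margin on the log10 scale is log10(1.5) = 0.1761.
- Power per strain = Phi(0.1761/0.03464 - 1.960) = Phi(3.123) = 0.9991.
- Four strains: 0.99911^4 = 0.9964, or 99.64%. The stated 99.6% reproduces.

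**2. SC power.** Exact binomial enumeration of the chance that the lower Wilson score (Newcombe) limit exceeds -10%, at 600 per arm:
- rate 0.5: 93.70%; rate 0.7: 96.66%
- four strains: 0.93701^2 x 0.96657^2 = 0.8203, or 82.03%

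The stated 93.7%, 96.7% and 82.0% reproduce.

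**3. Overall power by the plan's own multiplication.**

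| Inputs | Calculation | Result |
|---|---|---|
| Stated step powers | 0.996 x 0.820 | 0.8167 (81.7%) |
| Stated per-strain SC powers | 0.937^2 x 0.967^2 x 0.996 = 0.8210 x 0.996 | 0.8177 (81.8%) |
| Unrounded recomputation | SC 82.03% x GMT 99.64% | 0.8173 (81.7%) |
| Printed in both documents | | 82.0% |

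**4. Can rounding explain it?** Put both stated step powers at the top of their rounding intervals: 0.9965 x 0.8205 = 0.8176, or 81.8%. No pair of values that rounds to 99.6% and 82.0% has a product that rounds to 82.0%.

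**5. Bounds without independence.** Given the two stated step powers, the probability that both steps succeed is
- at least 0.996 + 0.820 - 1 = 0.816
- at most min(0.996, 0.820) = 0.820

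Joint power is therefore 81.6% to 82.0% under any dependence, and the overstatement is at most 82.0 - 81.6 = 0.4 points.

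**6. Sensitivity to dependence.** The documents give no correlation between the GMT and SC test statistics. Assume one value within every strain, bivariate normal statistics, independence across strains, and the powers from steps 1 and 2:

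| Assumed correlation | Overall power |
|---|---|
| 0 | 81.7% |
| 0.3 | 81.8% |
| 0.5 | 81.9% |
| 0.7 | 82.0% |

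**7. Consequence for the design.** Type II error = 1 - 0.8167 = 18.3%, below 20%. Replacing the Wilson score method by simpler approximations gives 81.3% (Farrington-Manning) or 81.0% (unpooled normal), both above 80%. Enrolment: 1200/0.85 = 1412, as stated.

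**The case against.** A reader might infer from the false equation that the design does not deliver the power claimed for it. The strongest reply has three parts.

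- **The prose says approximately.** To the nearest whole percent the recomputed power is 82%. This stands for the sentence. It does not rescue the parenthesis, which is an equation with one decimal on every term and is false at that precision.
- **The tests are probably not independent.** Seroconversion is derived from the same post-vaccination HAI titer that enters the GMT comparison (SAP 4.2.3.3), so positive dependence within a strain is to be expected. The simple product would then understate joint power, which could be as high as 82.0%. This stands, and it is why the headline figure cannot be called wrong as a statement about the design. It does not justify the printed line, which reaches its figure by multiplication and not by an argument from dependence. Multiplication is also the SAP's convention elsewhere: SAP 3.5.2.2 multiplies eight individual predictive powers, citing low correlations between strain titers. That reason concerns different strains, not the two tests on one strain.
- **The gap is smaller than the effect of the method chosen.** Moving from the Wilson score method to the approximations above changes overall power by up to about 0.7 points (81.7% to 81.0%). This also stands, and it limits the point to an editorial one.

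A reader might also infer that the SC figure was copied into the overall line, or that the GMT step was treated as free. The documents do not show how the number arose, so neither can be asserted.

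**Conclusion.** The printed calculation is wrong in both documents. Under the multiplication that the plan itself uses, overall power is about 81.7% (81.8% from the stated per-strain SC powers), which is 0.2 to 0.3 points below the 82.0% shown. That size rests on independence of the tests. Without that assumption, the stated step powers bound the overstatement at 0.4 points and allow it to be zero.

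All component powers reproduce. The criterion of Type II error below 20% is met, and the 1200 evaluable and 1412 enrolled are unaffected. No test, margin, analysis set or decision rule changes. The interim predictive power in SAP 3.5.2 is simulated from interim data and does not use this figure. This is a minor numerical correction, and it is not evidence that the trial is underpowered against its own target.

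**What to change.** In Protocol 9.2 and SAP 3.2, state the overall study power as approximately 81.7%, shown as 99.6% (GMTs) x 82.0% (SC), and add that the tests are taken as independent. Neither sample-size section states that assumption now. The following statement that power is above 80% can stay as it is.

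The cost is one figure and one short clause in each document, with a slightly less favourable stated power. Protocol 9.4 already provides for the SAP to be amended before any database lock, so the SAP correction can go in then, and the protocol correction can go with its next amendment.

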In the event of a local or national immunization program with any other vaccine as needed, participants who receive 1 or more doses of the vaccine listed above at any time during the study will not be withdrawn from the study.

9.4 Statistical Analyses

The SAP will be amended and finalized prior to any database lock (such as for interim and final analysis) and it will include a more technical and detailed description of the statistical analyses described in this section. This section is a summary of the planned statistical analyses of the most important endpoints including primary and key secondary endpoints.

9.4.1 General Considerations

The statistical analysis will be conducted as follows:

- At the end of the vaccination season of 2022-2023, after cleaning the database and fulfilling a partial database lock, the data in this study will be unblinded by an independent statistician to conduct an interim analysis. Safety summaries will be generated and separate PPoS of each of the 8 statistical tests will be calculated. The independent statistician will communicate and present the results to the FIC, who will make the decision of recommending or not recommending the stopping of the study. If the study continues the unblinded information from the 2022-2023 season will not be shared with the study team and the independent statistician will not be involved in the preparation and conduct of the study completion.
- The final database lock will occur after the 6-month follow-up period is completed for all subjects randomized and vaccinated in the study, or after stopping the study to write the final CSR.

The number of participants enrolled and their age at enrollment, sex, race, and ethnic origin will be summarized for each vaccine group, as well as the number and description of protocol deviations. In general, categorical variables will be summarized and presented by frequency counts, percentages, and confidence intervals (CIs). The 95% CIs of point estimates will be calculated using the normal approximation for quantitative data and the exact binomial distribution (Clopper-Pearson method) for percentages. For GMTs, 95% CIs of point estimates will be calculated using normal approximation of log-transformed titers.

Details will be provided in the SAP core body.

9.4.2 **Primary Endpoint(s)**

The immunogenicity parameters will be calculated in each study group with their 95% CIs using the exact binomial distribution (Clopper-Pearson method) for proportions and using normal approximation of log-transformed for GMTs.

Statistical Methodology for analyzing the primary 8 endpoints (GMTs and SC rates).

Non-inferiority of RIV4 as compared to IIV4 in participants 3 to 8 years of age will be conducted for GMTs and SC rates.

For each strain, the non-inferiority methodology will be applied to compare the post-vaccination GMTs and the SC rates between the groups using a 1-sided Type I error rate of 0.025 with the given individual hypothesis.

The primary analysis will be conducted into 2 steps starting with testing for NI of GMTs between RIV4 and IIV4. If NI of GMTs based on the 4 strains is demonstrated, then NI for SC will be also tested.

Step 1: Geometric Mean Titers

Assuming that log10 transformation of the data follows a normal distribution, the log10 (data) will be used for the statistical analysis, then antilog transformations will be applied to the results of calculations, in order to provide the results in terms of geometric means (GMs).

The statistical methodology is based on a 2-sided 95% CI of the ratio of the GMTs (RIV4 divided by IIV4) at 28 days after the last vaccination. Non inferiority for GMTs is demonstrated if the lower limit of the 2-sided 95% CI of the GMT ratio is > 0.667 for each of the 4 virus strains.

ANCOVA will be conducted for each strain with a model including the terms log10 of HAI titer at D01, priming status, age subgroup, season and the treatment represented by the vaccine administered as independent factors, and log10 HAI titer of each virus strain separately of the last vaccination as a response variable. ANCOVA will be conducted using Proc Mixed in SAS (all terms in the model are fixed). In Proc Mixed, the "Estimate" statement will allow to derive the difference (RIV4 minus IIV4) of the Least Squares-means and the 95% CI in their original log10 values. By exponentiating the difference (RIV4 minus IIV4) and its 95% CI; the 95% CI of ratio (RIV4/IIV4) will be obtained and be used to derive GMTs NI final results.

Step 2: Seroconversion

The statistical methodology will be based on a 2-sided 95% CI of the difference in SC rates (RIV – IIV4) 28 days after the final vaccination. Non-inferiority for SC will be demonstrated if the lower limit of the 2-sided 95% CI is > -10% for the 4 strains. The 95% CI of the rate difference will be computed using the Wilson Score method without continuity correction

Non-inferiority will be assessed on PPAS as the main analysis set and will be confirmed on the FAS.

As a sensitivity analysis, a generalized linear model (binomial-identity model) based on a link function named "identity link" will be used. The regression coefficient for the treatment (vaccines administered) in the binomial-identity model represent the proportions difference (difference between RIV4 and IIV4). The model will include priming status, age subgroup, season and the treatment term (represented by the vaccine administered) as independent factors. The difference (RIV4 – IIV4) and its 95% CI obtained will be used to derive the SC NI results.

In the sensitivity analysis, the statistical methodology will be based on a 2-sided 95% CI of the difference in SC rates (RIV4 – IIV4) at 28 days after last vaccination. The NI for SC rates will be demonstrated if the lower limit of the 2-sided 95% CI is > -10% for the 4 strains.

